## **6.3 Efficacy/Pharmacodynamic/Other outcomes - amended**

Main secondary endpoints will be assessed as:

Change from baseline to end of treatment (week 24) of:

- 6-Minute Walking Distance (6MWD)
- WHO functional class
- Lab N-terminal prohormone brain-type natriuretic peptide or brain-type natriuretic peptide (when both tests are available, NT-proBNP should be chosen over BNP and the same test should be performed at every required visit)
- Quality of Life scores (parent questionnaire and in children able to understand questions): Child Health-related Questionnaire (SF-10) and PedsQL Generic Core scales self-report
- Echocardiographic parameters including pulmonary arterial systolic pressure (PASP), right ventricular pressure by tricuspid regurgitant jet velocity, tricuspid annular plane systolic excursion (TAPSE), pericardial effusion, left ventricular eccentricity index, estimated right atrial pressure, acceleration time of the pulmonary flow, right heart dimensions, and computing of cardiac output.

Time to clinical worsening

- Hospitalization for right heart failure
- Death
- Lung transplantation
- Pott's anastomosis and atrioseptostomy
- Worsening of PAH symptoms, which must include either:
  - an increase in WHO FC
  - OR*
  - appearance/worsening symptoms of right heart failure
  - AND*
  - need for additional PAH therapy.

Other endpoints assessed in the study will be:

- Taste and texture of the pediatric formulation(s) must be assessed by use of a questionnaire at the beginning and at the end of treatment (week 24).
- Right heart catheterization

A change in RHC parameters (if available) obtained from RHC performed before study enrollment and during study conduct.

*(Note: The paragraph was modified according to Amendment 5, see Sections 17.2.1.2, 17.2.1.3 and 17.2.1.7. The Section was modified according to Amendment 6, see Sections 17.3.1.2, 17.3.1.3, and 17.3.1.6. This section was modified according to Amendment 9, see Sections 17.4.1.7 and 17.4.1.13.)*

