### **6.6.2 Data Monitoring Committee**

This independent committee has the responsibility to provide the SC and the sponsor with recommendations related to the protection of the subjects safety, including stopping recruitment and study treatment. For that purpose, the DMC will regularly review all incidences of serious adverse events and adverse events of special interest. Organizational aspects, responsibilities, and processes will be described in the DMC charter.

For all subjects reaching week 24 of the main study treatment phase and all subjects continuing in the LTE, the left hand x-rays will be evaluated by the DMC. The DMC will be provided with all relevant documentation on an ongoing basis.

After 5 patients in the  $\geq 12$  to  $< 18$  years old group have reached their optimal dose, have been treated on their maintenance dose and obtained the control x-ray of left hand at week 24, their data will be evaluated by DMC. After agreement of the DMC, the enrolment of patients in the age group  $\geq 6$  to  $< 12$  years will start.

All cases of clinical worsening (as defined in protocol section 6.3) that occur after intake of first dose of study medication in the main study treatment phase - including the 60 day safety follow-up period (only for those patients not entering the LTE) - will be evaluated by the DMC. After the completion of the main study, the DMC will be provided with all relevant documentation related to the cases.

Organizational aspects, responsibilities, and processes will be described in the DMC charter. DMC results will be included in the final analyses of the main study.

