## **8.1 Definitions**

### **8.1.1 Adverse event (AE) - amended**

An AE, including AE in relation to a medical device (i.e. Raumedic dosing pipette), is any untoward medical occurrence in a subject administered with a pharmaceutical product and does not necessarily have to have a causal relationship with this treatment. An AE can therefore be any unfavorable and unintended sign (including an abnormal laboratory finding), symptom, or disease temporally associated with the use of a drug, whether or not considered related to the drug. AE associated with the use of a drug, whether or not considered drug-related, includes AE occurring in the course of the use of a drug, from an overdose whether accidental or intentional, from drug abuse, from drug withdrawal, or if there is a reasonable possibility that the event occurred purely as a result of participation in the study, even if it is not related to the drug. AEs were considered to be treatment-emergent if they had started or worsened after the first dose of study medication up to 2 days after end of treatment with study medication. The clinical manifestation of any failure of expected pharmacological action is not recorded as an AE, if it is already reflected as an outcome captured in the eCRF, except if the event fulfills the criteria for a “serious” AE.

A surgical procedure or intervention that was planned prior to the study should not be recorded as an AE. Conditions, including abnormal physical examination findings, symptoms, and diseases will be recorded as medical history, if they started before providing written informed consent/assent. If the condition started or deteriorated after providing written informed consent/assent, it will be documented as adverse event.

Medical device related event is any occurrence or information the investigator becomes aware of regarding a medical device used in the study. Typical examples are:

- Malfunction, failure or deterioration in the characteristics or performance,
- An inaccuracy in the labeling or instructions for use,
- Use error.

*(Note: The text was modified according to the Amendment 3, See section 17.1.1.13.)*

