Right heart dimensions (i.e. Right atrial and Right ventricular)	Right atrial diastolic area index
	Right atrial systolic area index
	Right atrial diastolic area
	Right atrial systolic area
	Right ventricular diastolic area
	Right ventricular systolic area
	Right ventricular diastolic area index
	Right ventricular systolic area index
Cardiac output	Right Ventricular Cardiac Output
	Right Ventricular Cardiac Index

Assessments by Central Reader will be listed and analyzed descriptively by sample summary statistics. Time points of assessments are at baseline and week 24. Investigator’s assessments (Echocardiography Local) will be listed only.

Supplementary parameters (Diameter, vena cava inferior, baseline; Minimum inferior vena cava diameter; Left Ventricle-Short axis perpendicular; Left Ventricle-Short axis parallel; Pressure gradient of tricuspid valve; Respiratory collapsibility, v. cava inf.; right ventricular outflow tract – velocity time intergral; Right ventricular stroke volume; Heart Rate; Right

Ventricular Outflow Tract Area; Right Ventricular Outflow Tract Diameter) used to derive echocardiography parameters (Table 6–1) will be listed only.

• **Time to clinical worsening (TTCW):**

Time to clinical worsening is defined by the first of any of the following events:

- Hospitalization for right heart failure
(Preferred term (PT) as described in Table 6–2 AND requires or prolongs hospitalization = ‘Y’)
- Death (all cause mortality)
(all deaths during both treatment and follow-up period)
- Lung transplantation
(PT = ‘Lung transplant’)
- Pott’s anastomosis and/or atrioseptostomy
(Subject has either PT = ‘Systemic-pulmonary artery shunt’ OR PT = ‘Balloon atrial septostomy’ or both. The first event occurred will be considered.)
- Increase in WHO FC from baseline
- Appearance/worsening symptoms of right heart failure and need for additional PAH therapy (PT as described in Table 6–2 AND therapy as described in Table 6–3 at same day or up to 6 days before or after.)

Table 6–2: Right heart failure

Preferred Term (at least one must apply)
Acute right ventricular failure
Chronic right ventricular failure
Right ventricular failure
Pulmonary arterial hypertension

Table 6–3: Need for additional PAH therapy

Drug class	Compound (at least one must apply)
Endothelin receptor antagonist	Ambrisentan
	Bosentan
	Macitentan
Phosphodiesterase-5 inhibitor	Sildenafil
	Tadalafil
	Udenafil
Prostacyclin analogue	Beraprost
	Epoprostenol
	Iloprost
	Treprostinil

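### The TTCW rule in SAP 6.2.2 finds right heart failure through four diagnosis-level preferred terms and makes no use of the DMC evaluation, so events can be missed, dated late or wrongly counted

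*SAP*

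**What the plan says.** **Protocol 6.3** names TTCW among the main secondary endpoints. One component is "appearance/worsening symptoms of right heart failure" together with a need for additional PAH therapy. Hospitalization for right heart failure is a separate component. Neither is tied to a coding list.

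**SAP 6.2.2** restates the first component as "Appearance/worsening symptoms of right heart failure and need for additional PAH therapy (PT as described in" Table 6-2, with a Table 6-3 compound on the same day or up to 6 days either side. The Table 6-2 header reads "Preferred Term (at least one must apply", and four terms follow: acute right ventricular failure, chronic right ventricular failure, right ventricular failure, and pulmonary arterial hypertension. The hospitalization component uses the same table "AND requires or prolongs hospitalization".

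Two other SAP components need no adverse event term: "Increase in WHO FC from baseline" and death from any cause ("all deaths during both treatment and follow-up period"). Lung transplantation and shunt or septostomy have their own terms. Children without a derived event are right censored.

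**Protocol 6.6.2** has the DMC evaluate every case of clinical worsening, as defined in 6.3, after the first dose in the main phase, including the 60-day follow-up of children not entering the extension. It adds: "DMC results will be included in the final analyses of the main study".

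**SAP 4.4 and 6.2.2** send these cases and the TTCW output to the DMC. No step brings a DMC evaluation back into the derivation. SAP section 7 records an update to the definition of time to worsening without describing its content.

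**The concern.** The protocol component is about symptoms, while all four SAP terms are diagnoses. A right heart failure symptom recorded and coded as a symptom falls outside the list even when PAH therapy is added the same day. A hospitalization coded to a symptom fails its component too. In the other direction, the broad pulmonary arterial hypertension term lets a hospitalization count as one for right heart failure when no right heart failure occurred.

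The protocol also provides a case-level clinical evaluation of exactly these events, and the SAP's derivation leaves it out. What is at stake is whether the reported TTCW count and dates describe the clinical worsening that the protocol defines. With few children and no control arm, a handful of coding decisions can shape the result.

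**Working it through.** The documents give no TTCW event rate, target or power, so there is no planned figure to reproduce. The check compares the two rules and then sizes one misclassified case.

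**Step 1: four cases under both rules.** Cases 1 to 3 assume no death, transplant, shunt or septostomy.

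| Case | Protocol 6.3 | SAP 6.2.2 |
|---|---|---|
| 1. Symptoms coded as oedema, PAH therapy added, functional class not raised at Visit 9 | Event | No event; censored |
| 2. As case 1, functional class raised at Visit 9 | Event when symptoms and therapy occur | Event, through functional class, dated at Visit 9 |
| 3. Hospitalized for right heart failure, coded as dyspnoea | Event | Not by hospitalization or symptom-plus-therapy; only if functional class rises |
| 4. Hospitalized without right heart failure, coded as pulmonary arterial hypertension | Not a hospitalization for right heart failure | Event |

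**Step 2: how far functional class closes the gap.** Protocol 6.1.2.1, 6.1.2.2 and 6.1.3 schedule it at Visit 1 and at Visit 9 or the end-of-treatment visit. It is not among the unscheduled-visit procedures in 6.1.5. A rise that has resolved by Visit 9 can therefore be missed. For a rise that persists, the SAP formula is weeks = integer[(event date − start date + 1)/7]. Suppose symptoms begin 70 days after the start (an assumption): integer(71/7) = 10. If the event is picked up only at Visit 9, day 168: integer(169/7) = 24. It is dated 24 − 10 = 14 weeks late.

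**Step 3: size of one case.** Protocol 7.5 requires at least 20 children on an ERA. At n = 20 one case is 1/20 = 5 percentage points. Exact (Clopper-Pearson) 95% intervals:

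| Events | Proportion | 95% CI |
|---|---|---|
| 0/20 | 0% | 0 to 16.8% |
| 1/20 | 5% | 0.1 to 24.9% |
| 2/20 | 10% | 1.2 to 31.7% |

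**Step 4: chance that at least one case falls outside the list.** Let p be the share of children worsening by symptoms plus therapy and s the share of those coded outside Table 6-2. Both are assumptions. P(at least one) = 1 − (1 − p·s)^20.

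| p | s = 25% | s = 50% | s = 75% |
|---|---|---|---|
| 5% | 22% | 40% | 53% |
| 10% | 40% | 64% | 79% |
| 20% | 64% | 88% | 96% |

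The expected number is 20·p·s, from 0.25 to 3. As chances of losing an event altogether these are upper bounds, because a case outside the list can still enter through another component.

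**Step 5: do the observation windows match?** SAP 6.2.2 ends the main phase at Visit 9 for children continuing in the extension and at the safety follow-up visit for the others. The DMC evaluation in protocol 6.6.2 covers the main phase, plus the 60-day follow-up for children not continuing. The windows agree, so the DMC evaluation can serve as the event source.

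**The case against.** The strongest reply is that other components catch most real worsening. Functional class is also collected from children who stop early, any increase counts, and so does any death. This stands in part. A reader might infer that symptom-coded worsening never becomes an event, and the documents do not support that. Such a case is excluded only from these two components. What remains is the missed transient rise and the late date in Step 2.

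A reader might also infer that worsening escapes through the recording exemption in protocol 8.1.1: "The clinical manifestation of any failure of expected pharmacological action is not recorded as an AE, if it is already reflected as an outcome". The documents do not show this. The exemption reaches only outcomes that the case report form already holds, and serious events are outside it. The same section requires a condition that began or deteriorated after consent to be documented as an adverse event. The relevant outcome on the flow chart is functional class, and an increase there is itself an event. The eCRF was not available.

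It is fair, too, that protocol 6.6.2 speaks of evaluation and does not describe dated yes/no determinations. The DMC charter was not available and may contain a confirmation step. That limits what can be assumed about the DMC's output. It does not change the SAP rule, which stands complete without reference to any DMC finding.

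Finally, the pulmonary arterial hypertension term fits the protocol's heading of worsening PAH symptoms. That supports it in the symptom component, less so in hospitalization for right heart failure.

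**Conclusion.** The point holds within limits. Followed exactly, SAP 6.2.2 can miss, misdate or wrongly include events relative to protocol 6.3, and it does not carry out the protocol's statement that DMC results enter the final analyses. Each case is worth 5 percentage points at n = 20. If enrolment is larger, for example through children on prostacyclin analogues only, the step is 100/n.

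Two further inferences are not supported. One is that the result must look too favourable: cases 1 and 4 in Step 1 err in opposite directions, and the net effect is unknown. The other is that the decision to open the younger cohort was distorted. Under SAP 4.4 and 6.4.1 the DMC receives the clinical worsening cases themselves and listings of all adverse events. The current definition dates from SAP version 4.0 (17 JAN 2020), and nothing shows that it applied when the first five older children were reviewed.

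TTCW is exploratory and descriptive, with no test or event target, so error rates and sample size are untouched. The conclusion rests on the SAP text; the charter, eCRF and table shells could not be checked.

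**What to change.** In SAP 6.2.2:

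- Make DMC-evaluated events, assessed against protocol 6.3, the TTCW analysis. Specify the output needed for each case: event yes or no, component, and date.
- Use the preferred-term algorithm to find candidate cases and as a supportive analysis. Add medically reviewed symptom and sign terms to the candidate search.
- List every case on which the algorithm and the DMC evaluation disagree.
- Declare the change in SAP section 7.

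The cost is SAP text, a defined DMC output format, a small data transfer, and an event count that may differ from the algorithm's. No procedure is added for the children, and protocol 8.1.1 can stay as it is.

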4.1 General Principles

The statistical evaluation will be performed by using the software package Statistical Analysis Software (SAS) release 9.4 or higher (SAS Institute Inc., Cary, NC, USA). All variables will be analyzed by descriptive statistical methods.

1. The number of data available and missing data, mean, standard deviation (SD), minimum, 25% and 75% quartiles, median, and maximum will be calculated for metric data. Mean, median, quartiles and SD will be reported to one decimal place greater than the data were collected. Minimum and maximum values will be reported with the same precision as they were collected. The same metrics will be calculated for the change in parameters between Baseline and visits after Baseline.
2. Frequency tables will be generated for categorical data. These include the counts and percentages of each category including the category 'missing' as a separate category, if applicable. Percentages will be calculated using a denominator of all subjects in the specified population, and the percentage values will be reported to one decimal place. If an incidence is $< 0.1\%$ but $> 0\%$, it will be displayed as " $<0.1\%$ ".
3. If no data exists for a table, an empty table will be provided. The text in that table should read "No data matched the selected criteria".
4. For tables that fit horizontally on a single page, and that are more than one page in length, "Continued" will be added to the bottom of all but the last page. The word "Continued" must be added to the title for all pages after the first page and to the bottom of the page for all pages from the first to the second to last page.
5. For event-based tables the number of subjects should be displayed next to the treatment with the syntax "(N=x)". For tables where the N is the number of subjects and also used as the denominator "N=x (100%)" is to be used.
6. In frequency tables, if "n=0", then only "0" should be displayed; "(0.0%)" will not be displayed.
7. When numerator and denominator values are "0", do not use brackets. Use the following: "0/0", not "0/0 (%)".
8. All listings will be presented for subjects with their subject identifier, age at screening, sex and race.

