Prostacyclin agonist	Selexipag

TTCW will be analyzed descriptively by sample summary statistics.

All Kaplan-Meier estimates will be summarized.

In addition, Kaplan-Meier plots will be generated for the TTCW. Subjects without signs of worsening at the time of the main study or LTE phase analysis will be right censored at the date of end of main phase or the date of subject's study termination, whatever occurs first.

For subjects with event: Time to clinical worsening (weeks) = integer[(date of first event – treatment start date + 1) / 7].

For subjects without event: Time to worsening (weeks) = integer[(date study termination/ end of main phase – treatment start date +1) /7]. Date of study termination is defined as date of last visit. Date end of main phase is defined as date of the last visit of the main phase (Visit 9 for subjects continuing in LTE phase or safety follow-up visit for subjects not continuing in LTE phase).

TTCW will be part of the DMC package.

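### The sample summary statistics planned for time to clinical worsening do not estimate it, whether they pool event and censored times or use events only, and the whole-week truncation breaks the SAP's own rounding rule

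*SAP*

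**What the plan says.** SAP section 6.2.2 handles time to clinical worsening (TTCW) in four steps.

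- It names the summary: "TTCW will be analyzed descriptively by sample summary statistics". SAP section 4.1 sets out what descriptive statistics mean in this plan: "mean, standard deviation (SD), minimum, 25% and 75% quartiles, median, and maximum will be calculated for metric data". Protocol section 7.1 gives the same set for continuous variables.
- It then adds a censored-data analysis: "All Kaplan-Meier estimates will be summarized", and "In addition, Kaplan-Meier plots will be generated for the TTCW". Children without worsening "will be right censored at the date of end of main phase or the date of subject's study termination, whatever occurs first".
- It defines a value in weeks for both kinds of child: "For subjects with event: Time to clinical worsening (weeks) = integer[(date of first event" and so on, and "For subjects without event: Time to worsening (weeks) = integer[(date study termination/ end of main phase" and so on. In both, the days from treatment start, plus one, are divided by 7 and cut to an integer.
- It makes the end of the main phase depend on extension entry: "Visit 9 for subjects continuing in LTE phase or safety follow-up visit for subjects not continuing in LTE phase". SAP section 4.2 places the safety follow-up visit 60 ± 8 days after the last dose.

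The section does not say whether the sample statistics cover all children, only those with an event, or the Kaplan-Meier output. TTCW is part of the Data Monitoring Committee (DMC) package.

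**The concern.** A censored time is a lower bound on the time to worsening. A mean, SD or quartile that treats it as an observed time therefore describes follow-up as well as disease. Follow-up here differs by design: an event-free child who enters the extension stops contributing at Visit 9, and one who does not enter contributes for about 60 days more. Two groups with identical worsening could then show different means, and groups with different worsening could show the same one. SAP section 4.5 plans subgroups by age cohort and by background PAH medication. In a study of about 20 children, a difference in extension uptake between small subgroups could look like a difference in worsening.

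The truncation is a separate matter. It discards days from every time before any analysis is run.

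**Working it through.** The documents give no event rate, extension uptake or target figure for TTCW, so there is no planned number to reproduce. The check applies the SAP's own formula to an illustrative cohort.

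**Inputs from the documents**
- Formula: weeks = integer[(date − start + 1)/7] (SAP 6.2.2).
- Visit 9 at week 24, taken as 168 days after start (Protocol Table 0-1).
- Safety follow-up 60 days after the last dose (SAP 4.2).
- N = 20, the minimum number of children on an endothelin receptor antagonist (SAP 3.1).

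**Assumptions**
- Last dose at day 168 for children who do not enter the extension.
- Any event at day 84, and no censoring before Visit 9.
- Extension uptake among event-free children from 0% to 100%.

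**Value given to each child**
- Event: (84 + 1)/7 = 12.14, so 12 weeks.
- Event-free, enters extension: (168 + 1)/7 = 24.14, so 24 weeks.
- Event-free, does not enter: (228 + 1)/7 = 32.71, so 32 weeks. The ± 8 day window alone gives 31 to 33.

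**Pooled reading, no events at all**
- 20 enter: 20 × 24 / 20 = 24.0 weeks.
- 15 enter, 5 do not: (360 + 160)/20 = 26.0.
- 10 and 10: (240 + 320)/20 = 28.0.
- None enter: 20 × 32 / 20 = 32.0.

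The 8-week spread comes from the censoring rule alone. The Kaplan-Meier event-free probability at week 24 is 1.00 in every row.

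**Pooled reading, same mean with different worsening**

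| Events | Enter extension | Do not enter | Sum of weeks | Mean | Kaplan-Meier, week 24 (1 − events/20) |
|---|---|---|---|---|---|
| 0 | 20 | 0 | 480 | 24.0 | 1.00 |
| 2 | 15 | 3 | 24 + 360 + 96 = 480 | 24.0 | 0.90 |
| 4 | 10 | 6 | 48 + 240 + 192 = 480 | 24.0 | 0.80 |
| 6 | 5 | 9 | 72 + 120 + 288 = 480 | 24.0 | 0.70 |

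Events do move the pooled mean. With full uptake among event-free children it falls from 24.0 weeks (no events) to (6 × 12 + 14 × 24)/20 = 408/20 = 20.4 weeks (6 events).

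**Events-only reading.** With 2 events at day 84 the mean is 12 weeks, and with 6 events at day 84 it is also 12 weeks, while the Kaplan-Meier probability is 0.90 and 0.70. The mean ignores how many children worsened, and it cannot exceed the length of follow-up.

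**Truncation.** The remainder after division by 7 is 0 to 6 days, so each time loses up to 6 days. Study days 1 to 6 give integer[1/7] to integer[6/7] = 0 weeks. Against 24 weeks (168 days), 6 days is 3.6%. SAP section 4.5 defers rounding to the final presentation step and bars it within derived variables. SAP section 6.1.7 computes treatment duration as days divided by 7 with no integer function.

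**The case against.** The best case for leaving the text alone has four parts.

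1. **Pooling is not stated.** A reader might infer that the SAP commits to summarising event and censored times together. It does not say so. The phrase is stock wording, used also for echocardiography and nearly so for right heart catheterization, and could be a loose introduction to the Kaplan-Meier output. The formula for event-free children is needed for Kaplan-Meier in any case, so it does not prove pooling. This stands. Pooling is the natural reading, but not an explicit one. It does not rescue the sentence, however: pooled or events-only, the result does not estimate time to worsening, and if Kaplan-Meier is meant, the sentence duplicates the next one.
2. **A valid analysis is already planned.** This stands too. A reader might conclude that the mean is the SAP's only TTCW analysis, but the following sentences specify right-censoring, Kaplan-Meier estimates and plots.
3. **The mean still responds to events.** It would be wrong to say that it reflects follow-up and not worsening. As the 24.0 to 20.4 fall shows, it mixes the two.
4. **Little hangs on it.** No test or success criterion uses a TTCW mean, and under SAP section 4.4 the DMC receives documentation on each case of clinical worsening. The truncation applies alike to event and censored times, and no effect on a Kaplan-Meier estimate has been shown. This bears on severity, but it is no reason to keep the wording.

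**Conclusion.** The point holds as a minor correction. The sample-statistics sentence leaves its population undefined, and on neither reading that adds a table does it give a time to worsening. Under pooling, extension uptake alone can move the mean by 8 weeks in 20 children, and one mean value is compatible with week-24 event-free probabilities from 1.00 to 0.70. These sizes rest on assumed uptake, event counts and event timing. They show what the rule permits, not what the trial will observe.

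The truncation needs no interpretation: it contradicts SAP section 4.5 and costs up to 6 days per child. Severity is low because TTCW is exploratory in a single-arm, descriptive study and Kaplan-Meier is already specified.

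**What to change.** In SAP section 6.2.2:

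- Delete the sentence that applies sample summary statistics to TTCW.
- Keep the planned Kaplan-Meier analysis as the summary. Name the event-free probability at week 24, with its 95% confidence interval and the number at risk. The number at risk matters because the Visit 9 window is ± 5 days (Protocol Table 0-1), so some extension entrants can be censored just before week 24.
- Report the number and percent of children with an event.
- Compute time in days or unrounded weeks, and round only when the result is displayed.

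Carry the same change into the DMC outputs. The cost is SAP wording and the matching table specification. No data collection or visit changes.
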